VO ₂	respiratory oxygen uptake
VO _{2max}	respiratory oxygen uptake (max.)
VO _{2peak}	respiratory oxygen uptake (peak)
WBC	White blood cell

[figure not shown]
1 Introduction

The purpose of this document is to provide summary of the statistical methodology that will be used for this clinical study; this includes a detailed description of data summaries. Analysis plans in this document refer to the related statistical analysis sections in clinical study reports.

This Statistical Analysis Plan (SAP) module describes the statistical analysis according to Section 9 of the study protocol along with any additional analyses, specifications or deviations planned.

Data will be analyzed according to the data analysis section 9 of the study protocol which will be available in [Appendix 16.1.1 of the CSR](#). Important information is given in the following sections 2.7 (Analysis of secondary efficacy), 2.8 (Safety evaluation), 2.14 (Interim analysis) and 3 (Sample size calculation).

1.1 Study design

This study is a randomized, double-blind, double-dummy, parallel-group, active-controlled, two-arm, long-term trial to compare LCZ696 200 mg bid to enalapril 10 mg bid in improving exercise capacity, daily physical activity and quality of life in patients with stable CHF (NYHA III) and reduced ejection fraction (LVEF \leq 40%).

Eligible patients at stable dose of at least enalapril 10 mg/d or equivalent for at least 4 weeks before Visit 1 and LVEF \leq 40% can be randomized at Visit 3.

VO_{2peak} inclusion criterion will only be checked after assessment of patients' eligibility according to all other inclusion and exclusion criteria. Thus, ergospirometry will be performed on Visit 2 to get a complete assessment of CPET (for screening), [REDACTED]

Once patients' eligibility has been ascertained, they will attend Visit 3 for randomization approximately two weeks after Visit 1 to start enalapril 5 mg bid versus LCZ 100 mg bid for 2 weeks.

At baseline, all eligible patients will be randomized to receive either LCZ696 or enalapril in a 1:1 allocation during the double-blind period.

1.2 Study objectives and endpoints

[figure not shown]
1.2.1 Primary objectives

The primary objective of this study is to demonstrate the superiority of LCZ696 200 mg bid compared to enalapril 10 mg bid in improving exercise tolerance (VO_{2peak}, adjusted to body weight) as assessed by cardiopulmonary exercise testing (CPET) in patients with stable chronic heart failure (NYHA class III) and reduced ejection fraction (LVEF \leq 40%) after 3 months treatment.

1.2.2 Secondary objectives

Secondary objectives are:

- To demonstrate the superiority LCZ696 versus enalapril regarding improvement of exercise tolerance (VO_{2peak}, adjusted to body weight) as assessed by cardiopulmonary exercise testing (CPET) in patients with chronic heart failure after 6 weeks treatment.
- To compare LCZ696 versus enalapril on the following CPET parameters:
 - Change of VE/VCO₂ slope after 6 weeks and 3 months
 - Change in exercise capacity (Watt) at ventilatory anaerobic threshold (VAT) after 6 weeks and 3 months
 - Change in rate of perceived exertion during exercise (Borg Scale) after 3 month
- To assess the safety and tolerability of LCZ696 in patients with stable chronic heart failure with NYHA class III and reduced ejection fraction (LVEF \leq 40%)

2 Statistical methods

Descriptive statistics will be provided for all study variables. The descriptive statistics will include mean, median, SD, minimum, maximum, and 95% confidence interval of the mean, as needed for continuous scale variables and frequency distributions for categorical variables.

For categorical data, percentages will be rounded up to 1 decimal place. For continuous data, mean, and median will be rounded up to 1 additional decimal place compared to the original data. Standard deviation will be rounded up to 2 additional decimal places. Minimum and maximum will be displayed with the same accuracy as in the original data. Wherever changes from baseline will be used, change will be calculated as “post-baseline value – baseline value”. The number of decimal places for the “change from baseline” variables will be the same as for the original measurement.

2.1 Data analysis general information

Statistical Analysis System (SAS) version 9.4 or higher will be used to perform all the statistical analyses in the report.

2.1.1 General definitions

Patients who are eligible for randomization at Visit 3 will be assigned to one of the following two treatment arms in a 1:1 ratio.

- LCZ696 bid and placebo to match enalapril bid
- Enalapril bid and placebo to match LCZ696 bid

All randomized patients will receive either LCZ696 100mg or enalapril 5mg in a 1:1 allocation during the double-blind period at visit 3. Dose will be up-titrated after 2 weeks (Visit 4) to the final dose of enalapril 10mg bid or LCZ696 200mg bid. For allowed investigational treatment dose adjustments during double-blind period refer to Section 5.5.5 in the protocol.

Baseline: Baseline value is defined as the last non-missing assessment prior to the first dose of randomized study medication unless specified otherwise.

Post baseline: Any measurements taken after baseline will be considered as post-baseline measurements.

Change from baseline: Post baseline value – baseline value

Last contact: last contact will be the last time a patient's study record has been taken. For a patient who is still alive and in study the last contact will be his/her last clinical contact. For patient who died or is determined to be lost to follow-up before the analysis cut-off date, the last contact will be his/her death/lost-to-follow-up day.

Final Visit: Final visit will be the last time a patient's study record has been taken. For a patient who is still alive and in the study the final visit will be his/her last clinical visit. For a patient who died or is determined to be lost to follow-up before the analysis cut-off date, the final visit will be his/her death/lost-to-follow-up day. For a patient who is alive but no longer has regularly scheduled clinic visits and whose study records only can be obtained by telephone or indirect contact, the final visit will be the day the study records being taken.

2.2 Analysis sets

The following analysis sets will be defined for statistical analysis:

- Screened set (SCR) – All patients who signed the informed consent. The screened set includes patients based on their patient IDs assigned at each screening visit.
- Randomized set (RAN) - All patients who received a randomization number, regardless of receiving trial medication.
- Full analysis set (FAS) - The full analysis set (FAS) will consist of all randomized patients who have received at least one dose of study drug. Efficacy variables will be analyzed based on the FAS as the primary population.
- Safety set (SAF) - The Safety Set (SAF) will consist of all randomized patients who received at least one dose of study drug. The safety Set will be used for the analyses of safety variables.

2.2.1 Subgroup of interest

Not applicable.

2.3 Patient disposition, demographics and other baseline characteristics

Patient demographic and baseline characteristic data will be summarized based on FAS. Patient demographic and baseline characteristics include age, sex, and race. Relevant medical history/current medical condition, includes data until the start of study drug will be summarized. HF medications and other CV medications will be summarized separately from other medications. Likewise, detailed HF history and other relevant CV medical history will be summarized separately from other medical history.

2.3.1 Patient disposition

The number and percentage of patients enrolled, completed, and discontinued in the study and reason for the discontinuation will be summarized by treatment group. The reasons for screen failure will also be provided. All data will be listed. The analysis set will be FAS.

The number and percentage of the patients with protocol deviations as well as the criteria leading to exclusion from analysis sets will be presented for the FAS.

2.3.2 Demographic characteristics

Summary statistics will be provided based on FAS by treatment group for demographics and baseline characteristics, including age, age group (<65 years, >= 65 and < 85 Years, and ≥85 years), sex, race, weight, height, body mass index (BMI), category of prior CHF medication, prior HF hospitalization, NYHA class, and vital signs. BMI will be calculated as weight (kg) / (height (m))² collected at Visit 1 (Screening Visit).

Continuous variables will be summarized using n, mean, standard deviation, median, minimum, and maximum. Categorical variables will be summarized using frequency and percentage.

The following demographic variables will be analyzed:

- Age (years)
- Age group (<65 years, >= 65 and < 85 Years, and ≥85)
- Gender (Male, Female)
- Race (Caucasian, Black, Asian, Other)

The following baseline characteristic variables will be analyzed:

- Weight (kg)
- Height (cm)
- BMI (kg/m²)
- NYHA Class
- LVEF (%)
- Smoking History (Yes / No)
- Alcohol History (Yes / No)
- SBP
- DBP
- eGFR
- Prior CHF medication

2.3.3 Medical History

Any condition entered on the relevant medical history / current medical conditions CRF will be coded using the MedDRA dictionary. HF history and other CV medical history will be summarized.

The number and percentage of subjects with each medical condition will be provided by preferred term and system of organ class for the FAS.

The above medical conditions will also be listed.

Medical history possibly contributing to liver dysfunction and medical history possible related to statin will be summarized and listed separately based on FAS.

- **Heart failure History**

Heart failure history will be summarized by number and percent for following categories:

- Primary HF etiology (Ischemic /Non ischemic)
 - If Non ischemic:
 - Hypertensive (Yes/No)
 - Diabetic (Yes/No)
 - Alcoholic (Yes/No)
 - Viral cardiomyopathy (Yes/No)
 - Infectious cardiomyopathy (Yes/No)
 - Peripartum (Yes/No)
 - Drug induced (Yes/No)
 - Hypertrophic cardiomyopathy (Yes/No)
 - Idiopathic (yes/No)
 - Unknown (Yes/No)
 - Vitium (Yes/No)
 - If Yes, hemodynamically significant? (Yes/No)
 - Prior heart failure hospitalization(yes/no)
 - Number of hospitalization in the last 12 months
 - Ejection Fraction (%) in last 6 months

The heart failure history will also be listed for FAS.

- **Cardiovascular Medical history**

Cardiovascular history will be summarized by number and percent for following categories:

- Prior myocardial infection (Yes/No)
- Prior angina pectoris (Yes/No)

- If Yes, precise Angina Class (Class I, Class II, Class III, Class IV)
- o Did the subject have any prior PCIs? (Yes/No)
- o Did the subject have any prior CABGs (Yes/No)
- o Does the subject have a pacemaker? (Yes/No)
- o Does the subject have an ICD (Yes/No)

The cardiovascular history will also be listed for FAS.

Smoking history and alcohol history will be summarized in the separate tables based on FAS and will also be listed.

2.4 Treatments (study treatment, rescue medication, concomitant therapies, compliance)

2.4.1 Study treatment / compliance

The overall duration on the double-blind study drug will be summarized by treatment group using n, mean, standard deviation, median, minimum, and maximum. Additionally, the number and percentage of patients will be summarized by treatment group for duration category. The analysis will be based on the SAF.

Dose levels

Exposition to the different dose levels will be analyzed as patient numbers on the specified dose levels on visit 4, visit 6 and visit 7.

Doses and dose levels in the double blind phase as defined in the clinical study protocol are:

LCZ696: dose level 1 = 50 mg bid, dose level 2 = 100 mg bid, dose level 2a = 100 mg bid and dose level 3 = 200 mg bid.

Enalapril: dose level 1 = 2.5 mg bid, dose level 2 = 5 mg bid, dose level 2a = 10 mg bid, and dose level 3 = 10 mg bid.

Duration of double-blind study drug exposure will be calculated based upon the start and stop dates recorded in the eCRF.

- Last date of study drug – start date of study drug+ 1

2.4.2 Prior, concomitant and post therapies

Medications will be identified using Novartis Drug and Therapy Dictionary, NovDTD which is a modified Novartis internal version of Q3 2004 WHO Drug Reference List (DRL) including Anatomical Therapeutic Chemical (ATC) code.

The concomitant medication information for the double blind phase will be summarized based on the SAF.

Concomitant medications, significant non-drug therapies and surgical and medical procedures, prior to and after the randomization date respectively, will be summarized by treatment group based on the latest version of dictionary. Medications will be presented in alphabetical order, by ATC codes and grouped by anatomical main group (the 1st level of the ATC codes). Table

will also show the overall number and percentage of subjects receiving at least one drug of particular ATC code and at least one drug in a particular anatomical main group.

As before, concomitant medication will be identified based on recorded or imputed start and end dates of medication taking. The rules for imputing incomplete (start and end) dates are described in [Section 5.1.3](#).

Concomitant heart failure and CV medications administered during double blind period will be summarized separately, in the same way. More specifically, the following classes of medication will be summarized separately.

- Aldosterone antagonists
- β - blockers
- Ivabradine
- Diuretics
- Digoxin
- Other
- Statin
- ACEI
- ARBs

Below ATCs will be used to present ATC specific table for during and/or prior to study period:

ATC codes	Sub group	Sub sub group	Period
C CARDIOVASCULAR SYSTEM			Prior, During
	C01 CARDIAC THERAPY	C01A CARDIAC GLYCOSIDES	
		C01B ANTIARRHYTHMICS, CLASS I AND III	Prior, During
		C01C CARDIAC STIMULANTS EXCL. CARDIAC GLYCOSIDES	Prior, During
		C01D VASODILATORS USED IN CARDIAC DISEASES	Prior, During
		C01E OTHER CARDIAC PREPARATIONS	Prior, During
	C02 ANTIHYPERTENSIVES	C02A ANTIADRENERGIC AGENTS, CENTRALLY ACTING	Prior, During
		C02B ANTIADRENERGIC AGENTS, GANGLION-BLOCKING	Prior, During
		C02C ANTIADRENERGIC AGENTS, PERIPHERALLY ACTING	Prior, During
		C02D ARTERIOLAR SMOOTH MUSCLE, AGENTS ACTING ON	Prior, During
		C02K OTHER ANTIHYPERTENSIVES	Prior, During
		C02L ANTIHYPERTENSIVES AND DIURETICS IN COMBINATION	Prior, During
		C02N COMBINATIONS OF ANTIHYPERTENSIVES IN ATC-GR. C02	Prior, During
	C03 DIURETICS	C03A LOW-CEILING DIURETICS, THIAZIDES	Prior, During
		C03B LOW-CEILING DIURETICS, EXCL. THIAZIDES	Prior, During
		C03C HIGH-CEILING DIURETICS	Prior, During

		C03D POTASSIUM-SPARING AGENTS	Prior, During
		C03E DIURETICS AND POTASSIUM-SPARING AGENTS IN COMBINATION	Prior, During
		C03X OTHER DIURETICS	Prior, During
	C04 PERIPHERAL VASODILATORS		Prior, During
	C05 VASOPROTECTIVES		Prior, During
	C07 BETA BLOCKING AGENTS	C07A BETA BLOCKING AGENTS	Prior, During
		C07B BETA BLOCKING AGENTS AND THIAZIDES	Prior, During
		C07C BETA BLOCKING AGENTS AND OTHER DIURETICS	Prior, During
		C07D BETA BLOCKING AGENTS, THIAZIDES AND OTHER DIURETICS	Prior, During
		C07E BETA BLOCKING AGENTS AND VASODILATORS	Prior, During
		C07F BETA BLOCKING AGENTS, OTHER COMBINATIONS	Prior, During
	C08 CALCIUM CHANNEL BLOCKERS	C08C SELECTIVE CALCIUM CHANNEL BLOCKERS WITH MAINLY VASCULAR EFFECTS	Prior, During
		C08D SELECTIVE CALCIUM CHANNEL BLOCKERS WITH DIRECT CARDIAC EFFECTS	Prior, During
		C08E NON-SELECTIVE CALCIUM CHANNEL BLOCKERS	Prior, During
		C08G CALCIUM CHANNEL BLOCKERS AND DIURETICS	Prior, During
	C10 LIPID MODIFYING AGENTS	C10A LIPID MODIFYING AGENTS, PLAIN	Prior, During
		C10B LIPID MODIFYING AGENTS, COMBINATIONS	Prior, During
	C09 AGENTS ACTING ON THE RENIN-ANGIOTENSIN SYSTEM		Prior
		C09A ACE INHIBITORS, PLAIN	
		C09B ACE INHIBITORS, COMBINATIONS	Prior
		C09C ANGIOTENSIN II RECEPTOR BLOCKERS (ARBs), PLAIN	Prior
		C09D ANGIOTENSIN II RECEPTOR BLOCKERS (ARBs), COMBINATIONS	Prior
		C09X OTHER AGENTS ACTING ON THE RENIN-ANGIOTENSIN SYSTEM	Prior

2.5 Analysis of the primary objective

2.5.1 Primary endpoint

The primary endpoint is change of VO_{2peak} compared to baseline measurements (adjusted to body weight) after 3 months of treatment.

As per the protocol amendment, the primary variable changed from “ VO_{2peak} adjusted to lean body weight” to “ VO_{2peak} adjusted to body weight”. Furthermore, VO_{2peak} adjusted will be derived programatically as follows for the analysis:

$$\text{VO}_{2\text{peak}} (\text{adjusted}) = \frac{\text{VO}_{2\text{peak}} (\text{unadjusted})}{\text{Body weight}}$$

VO_{2peak} (adjusted) will be calculated at visit 2, 6 and 7 based on the every visit's VO_{2peak} (unadjusted) and weight data.

Efficacy analysis will be summarized based on FAS.

2.5.2 Statistical hypothesis, model, and method of analysis

The primary analysis will be performed using analysis of covariance (ANCOVA) model with treatment and center as factors and baseline VO_{2peak} as a covariate. The raw as well as the adjusted (LS) group means will be presented. Additionally, a 95% confidence interval and p-value will be presented for the treatment contrast.

Listing will be based on derived VO_{2peak} data.

2.5.3 Handling of missing values/censoring/discontinuations

Missing values of VO_{2peak} will be replaced with the last observed value (LOCF). Since the trial aims to estimate which improvements are achievable under the respective treatment regimens, LOCF seems to provide meaningful estimates for this purpose.

2.5.4 Supportive analyses

In case of deviations from the normality assumptions, treatments may additionally be compared by a non-parametric test (Mann-Whitney-U-test). In case of a substantial rate of missing data (>15%) or strong imbalances between treatment groups, Multiple Imputation (MI) may be considered as a sensitivity analysis.

2.6 Analysis of the key secondary objective

2.6.1 Key secondary endpoint

The key secondary endpoint is change of VO_{2peak} compared to baseline measurements (adjusted to body weight) at week 6. Efficacy analysis will be summarized based on FAS.

2.6.2 Statistical hypothesis, model, and method of analysis

The key secondary endpoint, the change from baseline in VO_{2peak} (adjusted to body weight) at week 6 will be analyzed similarly to the primary endpoint. The significance level will not be adjusted for multiplicity, the result of the test for week 6 will be regarded as providing confirmatory evidence, only if the test of the primary hypothesis (month 3) is also significant (a-priori ordered hypotheses).

2.7 Analysis of secondary efficacy objective(s)

2.7.1 Secondary endpoints

The following secondary endpoints will be analyzed:

- Change from in VE/VCO₂ slope after 6 weeks and 3 months
- Change in exercise capacity (Watt) at VAT after 6 weeks and 3 months
- Change in rate of perceived exertion (Borg Scale) during exercise after 6 weeks and 3 months

2.7.2 Statistical hypothesis, model, and method of analysis

Secondary efficacy variables will be analyzed using ANCOVA models analogous to the analyses of the primary endpoint.

2.7.3 Handling of missing values/censoring/discontinuations

Missing values will not be imputed and will be considered missing at that particular visit.

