*** Patients who prematurely discontinue study treatment should also return for the end of study (EOS) to collect at least safety assessments indicated by three asterisks (***).

**** To be documented at Visit 7 or at the time of premature discontinuation

1 Complete physical examination required at Visits 1, 2 and 7 (end-of-study visit). Short physical exam is sufficient at Visit 3 -6.

2 Qualifying LVEF measurements/documentation of structural heart disease will be based on obtained measurements (e.g. echocardiograms (echo)) performed ≤ 6 months prior to Visit 1. If an assessment performed ≤6 months prior to Visit 1 is not available, an echo must be performed during the screening epoch.

3 Women of childbearing potential only. At Visit 1 and 7 and in case of a positive urine pregnancy result, a confirmatory serum pregnancy test has to be performed at the central laboratory. A urine pregnancy test will be performed locally at Visit 2 and 7 and every time this is clinically indicated or a contraception gap has been reported.

4 Abbreviated chemistry panel including potassium, BUN, and serum creatinine will be measured at interim visits at the central laboratory.

5 Screening ECG performed within the 6 months before Visit 1 is accepted.

Phase		Screening		Double blind treatment**				
Visit	D/S*	1	2**	3**	4**	5**	6**	7/EOS***
Days(D)/ Weeks (W)		D-16 to -12 W-2	D-9	D1	D14 W2	D28 W4	D42 W6	D84 W12

9 At Visit 3 and 4, patients should come to the site 3 to 4 days prior to the scheduled visit date for blood draw only so that results from central laboratory are available and enable a competent decision on randomization or up-titration at the respective visits.

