9.4.3 Handling of missing values/censoring/discontinuations

Missing values of VO_{2peak} will be replaced with the last observed value (LOCF). Since the trial aims to estimate which improvements are achievable under the respective treatment regimens, LOCF seems to provide meaningful estimates for this purpose.

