9.5 Analysis of secondary variables

9.5.1 Efficacy variables

Secondary efficacy variables are:

- Change in VE/VCO_2 slope after 6 weeks and 3 months

- Change in exercise capacity (Watt) at VAT after 6 weeks and 3 months
- Change in rate of perceived exertion during exercise (Borg Scale) after 6 weeks and 3 months

Secondary efficacy variables will be analyzed using ANCOVA models analogous to the analyses of the primary endpoint.

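### Month-3 secondary CPET endpoints drop patients whose VO2peak from the same test schedule is carried forward, and leave their week-6 data unused

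*SAP*

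**What the plan says.** **Secondary CPET variables.** SAP 2.7.1 lists VE/VCO2 slope, watts at VAT and Borg, each at 6 weeks and 3 months. SAP 2.7.3 states: "Missing values will not be imputed and will be considered missing at that particular visit". Protocol 9.5.1 gives these variables no missing-data rule of its own, only a model: "Secondary efficacy variables will be analyzed using ANCOVA models analogous to the analyses of the primary endpoint". SAP 2.7.2 repeats that sentence.

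**VO2peak.** SAP 2.5.3 states that missing VO2peak "will be replaced with the last observed value (LOCF"). Protocol 9.4.3 has the same rule and justifies it by the aim of estimating achievable improvement: "LOCF seems to provide meaningful estimates for this purpose". The key secondary, VO2peak change "at week 6 will be analyzed similarly to the primary endpoint" (SAP 2.6.2), so it falls under LOCF and not under SAP 2.7.3.

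**Model and population.** The primary ANCOVA has "treatment and center as factors and baseline VO_{2peak} as a covariate" (SAP 2.5.2). Efficacy is analysed on the FAS, which requires randomization and one dose but no post-baseline test (SAP 2.2).

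**Sensitivity analysis.** Optional multiple imputation appears under the primary objective only (SAP 2.5.4). None is listed for the secondaries.

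**Testing after study drug is stopped.** Protocol 5.5.10 has such patients continue all scheduled visits and procedures. The Table 6-1 footnote (protocol section 6) asks them to return "to collect at least safety assessments indicated by three asterisks". Ergospirometry and Borg at Visit 7 carry a plain x without asterisks.

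**The concern.** All these variables come from one ergospirometry, taken at Visits 2, 6 and 7. The SAP treats a missing test in two ways depending on which variable is read from it, and gives no reason. SAP section 4, on changes to the protocol analyses, does not mention the rule either.

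Two things follow at month 3. First, the primary and secondary results can rest on different patients although both are labelled FAS, so agreement or disagreement between them may partly reflect data handling. Second, a patient's week-6 secondary value, which may predict both the missing test and the missing result, plays no part in the month-3 contrast. If patients who respond poorly or tolerate treatment badly tend to miss the month-3 test, the month-3 contrast among those tested need not be the contrast among those randomized.

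**Working it through.** **1. The plan's own figure.** Inputs from protocol 9.7 and SAP 3: difference 1.5, SD 3, two-sided 5%, power 90%. Normal approximation: n = 2 × (1.960 + 1.282)² × 3² / 1.5² = 84.1, so 85 per arm. The two-sample t-test gives power 0.8999 at 85 and 0.9032 at 86. The stated 86 is reproduced, and it does not depend on the missing-data rule.

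**2. How many patients could be affected.** No drop-out rate is stated. The step from 86 to 100 per arm implies 1 − 86/100 = 14%. If every one of these missed the month-3 test and had an earlier value to carry forward, up to 14 per arm (28 of 200) would be in the month-3 VO2peak analysis but not in the month-3 secondaries. An assumed 10% to 20% gives 20 to 40 of 200. These are ceilings: the allowance also covers other protocol deviations, and neither document says whether baseline is carried forward when no post-baseline test exists.

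**3. Does unequal drop-out alone bias the planned ANCOVA?** Simulation with baseline-adjusted ANCOVA, 2000 per arm, 300 runs, Monte Carlo standard error about 0.006. Assumed: true difference 1.5 at both visits, SD 3, week-6/month-3 correlation 0.6. Rates are LCZ696 vs enalapril.

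| Drop-out | Complete-case | Full data |
|---|---|---|
| 10% vs 20%, unrelated to response | 1.50 | 1.50 |
| 20% vs 10%, unrelated to response | 1.49 | 1.49 |
| 13% vs 23%, dependent on baseline | 1.51 | 1.51 |

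It does not. Nor are unequal rates needed for bias: with 19% drop-out in each arm but opposite selection on week-6 response, an extreme case, complete-case analysis gave 0.82 (full data 1.50).

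**4. Drop-out related to week-6 response.** Assumed: true month-3 difference 1.5, SD 3, week-6/month-3 correlation 0.7, week-6 difference 1.0, logistic drop-out on week-6 response, baseline-adjusted ANCOVA. Rate pairs: 10% vs 18%, 7% vs 21% and 18% vs 10%. Ranges run across the pairs.

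| Dependence on week-6 response | Complete-case | Using week-6 data |
|---|---|---|
| None | 1.49–1.51 | about 1.5 |
| Log-odds 0.5 per SD (moderate) | 1.38–1.58 | about 1.5 |
| Log-odds 1.0 per SD (strong) | 1.29–1.62 | about 1.5 |
| Strong, half of drop-outs lost before week 6 | as in the row above | 1.41–1.55 |

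The largest shift shown is 1.5 − 1.29 = 0.21, which is 0.21/1.5 = 14% of the effect and 0.21/3 = 0.07 SD. The mirror pair, 21% vs 7%, was not in the set. By symmetry it would give roughly 1.5 + 0.21 = 1.71.

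**5. Size against sampling error.** With 86 per arm the standard error of the difference is 3 × √(2/86) = 0.46, so 0.21 is about 0.46 of one standard error.

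**6. Can the two rules move apart?** With the step 4 set-up at 18% vs 10% and log-odds 0.25 to 0.5 per unit (0.75 to 1.5 per SD), complete-case analysis gave 1.61–1.68 and LOCF 1.36–1.37. The gap is 1.61 − 1.37 = 0.24 to 1.68 − 1.36 = 0.32, from data handling alone.

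**The case against.** The strongest defence is that a baseline-adjusted complete-case ANCOVA is a legitimate analysis. It is unbiased when missingness depends only on arm, center and baseline. A reader might infer that the secondaries are biased whenever drop-out differs between arms; step 3 shows that this does not follow.

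A reader might also infer from the Table 6-1 footnote that stopping treatment means losing the month-3 test. The documents do not establish that. The footnote sets a minimum, and protocol 5.5.10 keeps such patients in all procedures. The two passages differ, so how many tests would be missing, and in whom, is unknown.

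The size is also open to challenge. The strength of the link to week-6 response and the correlation between visits are assumptions. The scale is that of VO2peak, because the documents give no effect or SD for VE/VCO2 slope, watts or Borg. In the main scenarios missingness is generated from an observed week-6 value, so a method using that value recovers 1.5 by construction. Finally, the week-6 secondary values are not discarded: they have their own week-6 analysis.

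All of this stands and limits the claim. It does not explain why one test follows two rules, supply a missing-data sensitivity analysis for the secondaries, or justify leaving collected week-6 data out of the month-3 estimate.

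**Conclusion.** The inconsistency is real, and the per-visit complete-case rule is weaker than an available alternative. The possible bias is conditional on response-related missingness. Under the assumptions of step 4 it is about 0.1 with moderate dependence and about 0.2 with strong dependence, in either direction, on a difference of 1.5. More extreme selection would give more; the documents give no means of saying how likely that is.

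Two further readings are not supported. One is that the secondaries will rest on 86 per arm against 100 for the primary. That treats the whole allowance as missing tests, although SAP 5.5 keeps patients with nearly all types of deviation in the FAS. The other is that LOCF is the sound benchmark from which the secondaries depart. With drop-out unrelated to response, half of it before week 6 with baseline carried forward, LOCF gave 1.43 (10% vs 20%) and 1.34 (20% vs 10%) where complete-case analysis gave 1.50 and 1.49.

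Confirmatory claims are confined to VO2peak at month 3 and week 6 (protocol 9.4.2, SAP 2.6.2), which SAP 2.7.3 does not govern. Severity is low to moderate.

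**What to change.** Replace SAP 2.7.3 with an MMRM for each secondary CPET variable measured at weeks 6 and 12 (VE/VCO2 slope, watts at VAT, Borg). Terms: treatment, center, visit, treatment-by-visit, the variable's own baseline and baseline-by-visit, with an unstructured covariance. Report the treatment contrast at each visit and state the missing-at-random assumption. Keeping center preserves the planned factor.

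Do not extend LOCF to these variables. Whether VO2peak should keep LOCF is a separate matter that touches the protocol's primary analysis.

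Reconcile protocol 5.5.10 with the Table 6-1 footnote on whether ergospirometry is expected after study drug is stopped.

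The cost of the model change is SAP text and code in a procedure the SAP already uses (PROC MIXED, SAP 5.4.1), with no new data. The small downside is that a covariance structure and a missing-data assumption must be specified. The model helps less for patients lost before week 6.
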